stimulating the growth and/or activity of one or a limited number of bacteria in the colon, thus improving host health" [20]. These supplements are effective in reducing the severity and duration of infectious diarrhea [21], as well as improving bowel regularity. Prebiotics may also improve intestinal permeability and gut inflammation - two factors which have been linked to obesity and metabolic syndrome [22, 23]. However, prebiotic supplements, when used in isolation, could increase flatulence by producing methane and hydrogen sulfide gas as byproducts via methanogen and sulfate-reducing bacteria, respectively (Figure 2) [24]. To decrease these unwanted side effects, preliminary studies have demonstrated that using polyphenols -- naturally occurring compounds that are metabolized by the SCFA-producing bacteria (acetogens)-- may be helpful in reducing flatulence (Figure 2) [25]. The presence of polyphenols, commonly found in fruits and vegetables, allows acetate-producing bacteria to thrive, while methane- or hydrogen sulfate-producing bacteria have less available hydrogen substrate to convert to their respective gases [25, 26]. In a pilot randomized trial of 10 adults with T2D, a prebiotic microbiome modulator (MM) with inulin and beta glucan plus polyphenols from blueberry pomace improved metformin tolerability and fasting glycemia [27]. This same cocktail improved glucose profiles in healthy adults with overweight and obesity during an oral glucose tolerance test [28]. However, the mechanisms by which prebiotics influence metformin-induced GI side effects are unknown. Importantly, it remains to be established whether using this supplement is feasible in youth and young adults with T2D, whose microbiome signatures may be different from adults [29]. This study is innovative and clinically significant because it uses a prebiotic intervention to evaluate gut-incretin pathways while identifying whether a relatively safe supplement could

improve quality of life and glycemia in youth and young adults with type 2 diabetes who are high-risk for diabetesrelated complications.

Preliminary studies:

Currently, we are exploring metformin's mechanism of action in African American youth with T2D (NCT02960659), including changes in their microbiome. Our preliminary findings from 4 youth who were evaluated before and after 3-months of metformin therapy showed a decreasing trend for HbA1c (-0.56±0.2%) and increasing trends for stool

[figure not shown]

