Participants will receive instructions on stool collection at home and stool collection kits - one to be mailed back to the study team for analysis prior to stopping their baseline metformin dose (unless they are able to provide a stool sample after consent while still at NIH), and one to collect a sample in the 24 hours prior to visit 2 if has a bowel movement. Patients will also be taught how to fill out daily surveys to assess GI symptoms (see details below). They will meet with a member of the nutrition team to select foods for their metabolic diet and to be educated on completing a 3-day food record. Participants will also be educated on foods we will ask them to avoid during the study, such as pre/pro-biotics (kombucha, kefir, yogurt, etc.) and foods containing non-nutritive sweeteners.

Period 1 (Drug-free run-in, Visit 2 and 3)

Drug-free run-in period: Participants will discontinue metformin for the 7-10 days preceding Visit 2, to assess their metabolic and gut microbiome response off anti-diabetic medications, as well as to wash out the immediate effect of metformin on the participants microbiota. The timing of this 1 week period was chosen because changes in gut microbiome have been observed in as little as 1 day and on average 1 week [33]. During this time, participants will complete daily GI symptom questionnaires and monitor their blood glucose and upload their readings daily while not taking metformin. Participants with persistently elevated fasting glucose readings and/or signs and symptoms of metabolic decompensation (e.g. vomiting, dehydration, lethargy, abdominal pain, ketonuria and acidosis) will be withdrawn from the study and restarted on his/her medication. During the drug-free run-in period, individuals who cannot either wear the continuous glucose monitor (CGM), or complete at least 2 finger stick blood glucose measurements daily will be withdrawn from the study.

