Visit 2: This visit will take place 7-10 days after discontinuing metformin. Study personnel will review dosing and the completeness of GI questionnaires, as well as glucose trends with the participants. Participants will leave with a study metformin supply from the NIH pharmacy, as well as bottles of either placebo or prebiotic for a 1 week +15% supply and be instructed to take metformin and the powder mixed with a shake provided by the study team at the same time twice daily, with the first dose given with dinner that evening. Participants will take metformin 850mg with dinner on day 1-3and the dose will be increased to 850mg with breakfast and with dinner on day 3 and thereafter. Participants will fill out daily GI symptom questionnaires and will be instructed to contact the NIH study team if they are unable to tolerate the medication. Participants will be provided with 1 week of food to take home and consume on the week prior to Visit 3. The NIH Clinical Center Metabolic Kitchen will pack out meals for 7 days. Energy provided will be estimated using Mifflin St Jeor equation and an activity factor of 1.3 [34]. Participants will also leave with an accelerometer to be worn around the wrist 24 hours/day during the period between visits 2 and 3.

Visit 3: Participants will return to the NIH CC 7-9 days after visit 2. Stool and urine sample collection and bottle/ pill counts and assessment of uneaten food will be performed, and the accelerometer will be returned. Participants will undergo a MMT (see description below). Completeness of GI symptom questionnaires and glucose trends will be reviewed.

Period 2 (Washout, Visit 4 and 5)

Participants will be instructed to stop taking all metformin and MM/placebo powder during the washout period between visit 3 and 4; instructions for CGM and hyperglycemia precautions that were given at the screening visit will be reviewed with the family. The 2-3 week washout was chosen to minimize any carry-over effects and has been optimal for detecting gut microbiota after discontinuing therapy [9, 27].

Visit 4: Visit 4 will occur at the NIH CC 14-24 days after the beginning of the wash out period; The NIH Clinical Center Metabolic Kitchen will pack out frozen and non-perishable items to provide meals for 7 days. Participants will also be asked to wear the accelerometer on wrist until they return for visit 5.

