3.2.1 Study Procedures

- **GI symptom questionnaires**: A questionnaire derived from validated sets used for GI symptoms of irritable bowel syndrome [35] which previous investigators have used [27]. Assessments of stool consistency (not applicable, very hard, hard, formed, loose, watery), urgency to evacuate (no need to evacuate within 3 hours after dosing, need to evacuate within 3 hours, need to evacuate within 2 hours, need to evacuate within 1 hour), daily bowel movements (at least 1 movement every 3-4 days, at least 1 movement every 2 days, at least 1 movement per day, at least 2 movements per day), bloating sensation (not applicable, mild, moderate, severe), flatulence (less than normal, normal, moderately increased, greatly increased), and evacuation completeness (not applicable, incomplete, constipated), in addition to a King's stool chart, will be included (see Appendix A) [27]. This survey will be available in an online platform designed for mobile device but may also be filled out in paper form.

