- **Blood glucose monitoring**: Blood glucose will be monitored with either fingerstick blood glucose twice daily (fasting and bedtime) or by using an FDA- approved continuous glucose monitoring device (CGM) (for example, the Freestyle Libre). The device will be used to monitor glucose in real-time, approximately every 5 minutes. The system consists of a small sensor, transmitter, and hand-held receiver. The small sensor, with a small needle attached, will be inserted subcutaneously. The transmitter, which is attached to the sensor, will send the measured glucose to the receiver. The sensor is changed at least once every two weeks. Participants will receive training on removing and replacing the sensor and education on the signs and symptoms of hyperglycemia (see Appendix B). Participants will be asked to upload their readings daily to be monitored by a member of the study team daily while participants are not taking metformin, and weekly while taking metformin. Participants will be asked to contact the study team immediately after confirming with a finger stick BG if their glucose is low (<50mg/dL), or if they have a fasting blood glucose reading of >200mg/dl, or a reading anytime of >300mg/dl. Participants with persistently elevated fasting glucose readings and/or signs and symptoms of metabolic decompensation (e.g. vomiting, dehydration, lethargy, abdominal pain, ketonuria and acidosis) will be withdrawn from the study and restarted on his/her medication.

- Activity and Sleep Monitoring: Free-living physical activity and sleep quality will be quantified using a small, non-invasive, portable watch accelerometer (GT3X+ by Actigraph Inc., Pensacola FL) worn on the participant's wrist. Physical activity levels, sleep duration and efficiency, amount of time spent in sedentary, moderate, vigorous intensity categories and estimated activity-associated energy expenditures will be extracted using established predictive equations. This is an FDA 510(k) cleared Class II medical device.
- Urine sample collection: urine will be collected at every visit for storage; for females, this same sample will be used for a pregnancy test
- **Stool sample collection:** Participants will bring stool samples from home collected in the previous 24 hours to be processed by the study team or stool samples will be collected during outpatient visits. The stool sample will be stored at 4C in a sterile plastic vial and processed same day (see Appendix C).

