5.2 Analysis of Primary and Secondary Outcomes

The primary outcome, the participant's composite score of tolerability will be constructed using the principal component analysis (PCA) based on 4 GI side effect profile categories (stool consistency, urgency to evacuate, bloating sensation, and flatulence). PCA will be used to account for the expected high inter-patient variability. Comparison of mean tolerability score over 1 week will be with linear mixed models, adjusting for baseline score. Pre-specified covariates are: treatment period and sequence effects from the cross-over design.

The secondary outcome, change in mean stool SCFA over 1 and 4 weeks, will be analyzed using repeated measures of analysis variance (ANOVA) to consider correlation of observations within each participant. Participant and exploratory characteristics will be expressed as mean and standard deviation, median and interquartile range for continuous variables and frequency for categorical variables. Between group comparison of means will also be analyzed using repeated measures ANOVA. Spearman correlations will be used to compare relationships between continuous variables. A P-value of <0.05 will be used for statistical significance.

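### Stool SCFA can be measured only if a stool is passed within 24 hours before a visit or on site, and the plan has no missing-sample rule and an analysis that may discard incomplete participants

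*Combined protocol and SAP*

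**What the plan says.** Section 2.1 makes stool propionate and butyrate after 1 and 4 weeks the secondary outcome. Table 1 schedules a stool sample at Visits 2 to 6.

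Section 3.2.1 gives two routes to a sample. The first is a home sample: "Participants will bring stool samples from home collected in the previous 24 hours to be processed by the study team". The second route, given as the alternative in the same sentence, is on site: "or stool samples will be collected during outpatient visits". It requires storage at 4C and processing on the same day. Section 4.1 allows less than 24 hours at 4C before transfer to -80C.

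The plan expects that a stool may not be available. In section 3.2 the second kit given at screening is "one to collect a sample in the 24 hours prior to visit 2 if has a bowel movement". The bowel-movement item of the GI questionnaire in 3.2.1 includes the levels "at least 1 movement every 3-4 days, at least 1 movement every 2 days, at least 1 movement per day".

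On timing, section 3.2 says "Participants will return to the NIH CC 7-9 days after visit 2". Table 1 gives the same 7-9 days for Period 2, and Visit 4 falls 14-24 days after washout begins.

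On analysis, section 5.2 assigns SCFA to "repeated measures of analysis variance (ANOVA) to consider correlation of observations within each participant", whereas the primary outcome gets linear mixed models with period and sequence as covariates. The text available states no substitute sample for Visits 2-6, no rescheduling tied to stool, and no rule for missing samples.

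**The concern.** Whether an SCFA value exists at a visit depends on how often the participant passes stool, which is part of the gut state under study. It may also depend on treatment: section 1.0 credits prebiotic supplements with "as well as improving bowel regularity", and section 3.5 expects the placebo to leave stool frequency unchanged. If the prebiotic (MM) alters frequency in either direction, the samples available under MM and placebo would come from somewhat different sets of participants.

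The analysis can add to the loss. In its conventional form, repeated measures ANOVA uses only participants with a complete set of the visits in the model. A participant with both end-of-period samples, which carry the MM-placebo comparison at 1 week, could be removed for a missing stool at another visit. Section 5.1 expects about 10 completers, so each such removal costs about a tenth of the data.

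**Working it through.** **The plan's own figure.** Section 5.1 states 90% power for SCFA with 20 participants, alpha 0.05 and correlation 0.5. With correlation 0.5, the SD of a within-person difference is SD × √(2(1 − 0.5)) = SD. Taking alpha as two-sided, which the plan does not state, power ≈ Φ(d√n − 1.96).

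- Butyrate: d = 4.17/5.72 = 0.729; with n = 20, Φ(3.26 − 1.96) = 90.3%.
- Propionate: d = 2.95/3.3 = 0.894; with n = 20, 97.9%.

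The stated 90% is therefore reproduced for butyrate, the weaker of the two, if all 20 participants give complete pairs.

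**Chance of a sample.** The home window is 24 hours (3.2.1). Time on site is not stated, so 0-6 hours is assumed; the mixed meal test at Visits 3 and 5 alone lasts 180 minutes. Assume evenly spaced stools and visits timed without regard to them. Then p = window/interval, with a window of 24 to 30 hours. The chance at both Visits 3 and 5 is p², and at all of Visits 2-5 it is p⁴.

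| Stool interval | One visit, p | Visits 3 and 5, p² | Visits 2-5, p⁴ |
|---|---|---|---|
| Daily | 100% | 100% | 100% |
| Every 2 days | 50-63% | 25-39% | 6-15% |
| Every 3 days | 33-42% | 11-17% | 1-3% |
| Every 4 days | 25-31% | 6-10% | 0.4-1% |

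**Loss of Visit 3/5 pairs.** The documents do not say how many participants have less than daily stools. Assume 10-30%, all at every 2 days. Loss = share × (1 − p²).

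- 24-hour window: 0.10 × 0.75 = 7.5%; 0.30 × 0.75 = 22.5%.
- 30-hour window: 0.10 × 0.61 = 6.1%; 0.30 × 0.61 = 18.3%.

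The range is about 6-23%.

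**Effect on butyrate power (same formula).**

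- From 20 participants: 15.5 to 18.8 expected pairs, power 82-88%, against 90.3% with no loss.
- From 10 completers: power is 63.5% before any missed stool. With 7.75 to 9.4 expected pairs it is 53-61%.

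**Extra loss from complete-case ANOVA.** Section 5.2 does not say which visits enter the model. If Visits 2-5 all did, a participant with stools every 2 days would have the Visit 3/5 pair but lack Visit 2 or 4 with probability p² − p⁴: 0.25 − 0.06 = 0.19 (24 hours) to 0.39 − 0.15 = 0.24 (30 hours). With the same 10-30% share, the total loss becomes share × (1 − p⁴), or about 8-28%, instead of 6-23%.

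**The case against.** A reader might infer that participants with infrequent stools drop out by design. The documents do not support that. On-site collection is a second route, a missed sample is not a withdrawal criterion in 9.3.1, and at every 2 days the chance of a sample at a visit is at least one half. What is lost is SCFA data, and only with some probability.

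A reader might also infer that placebo would lose more samples than MM. That direction is not supported either. The phrase in 1.0 concerns prebiotics in general, and no MM effect on frequency is quantified. Visits 3 and 5 both follow about a week of metformin, which the background says can cause diarrhea. MM is hypothesised to reduce lower-GI effects, so it could lower frequency relative to placebo, while 8.5.2 lists loose stools as an uncommon effect of MM.

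Other points on the plan's side have weight. The questionnaire levels show that infrequent stools are foreseen, not how common they are, and 3.3.2 excludes chronic GI disease. Visit windows leave room to time a visit, although nothing says they will be used for this. Section 5.2 does not specify complete-case deletion, and software may handle incomplete sets differently. Appendix C, cited for stool processing, was not available and might contain a fallback. Finally, the planned 50% attrition costs more power (90.3% to 63.5% for butyrate) than missed stools do in these scenarios.

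These points limit the size and direction of the problem. The silence on missing samples in 5.2 remains.

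**Conclusion.** The concern holds as a gap in handling missing SCFA data. Some samples will be missing in a way related to stool frequency and possibly to treatment, with unknown direction. If 10-30% of participants have stools every 2 days, about 6-23% of Visit 3/5 pairs are lost. The range rests on even spacing, random visit timing, 0-6 hours on site and the assumed share. Less frequent stools would enlarge the loss; visits timed to stool availability would reduce it.

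Conventional repeated measures ANOVA could add to this by discarding participants who have that pair. The consequence is moderate: this is a secondary outcome in a pilot, but with about 10 completers there is little data to spare. Neither exclusion by design nor greater loss on placebo follows from the documents.

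**What to change.** **Analysis (5.2).** Replace repeated measures ANOVA for SCFA with a linear mixed model with a participant random effect and fixed treatment, period and sequence, in line with the primary outcome. State which visits enter it. Participants with some samples are then kept. The model does not restore lost pairs, and its estimates rest on samples being missing at random given the observed data. The number of missing stool samples should therefore be reported by treatment and visit.

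**Collection (3.2 and 3.2.1).** State that Visits 3 and 5 (7-9 days) and Visit 4 (14-24 days) will be timed to stool availability within those windows where possible. Confirm that dispensed powder and packed meals last to the later days.

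**Older samples.** A home-frozen earlier stool should be considered only if it is shown to be compatible with the handling in 3.2.1 and 4.1 (4C, same-day processing, under 24 hours before -80C). Otherwise sample handling would itself vary with stool frequency.

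The cost is a few sentences in 5.2, one table and some scheduling effort, with no extra visit.

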3.3 Inclusion and Exclusion Criteria

3.3.1 Inclusion Criteria

- 1. Age 10-25 years
- 2. Pubertal or post-pubertal: Girls Tanner stage IV-V breast; Boys Testicular volume >10cc
- 3. Diagnosis of type 2 diabetes by ADA guidelines [36] or with established diagnosis previously treated with metformin.
- 4. Negative test for diabetes-related autoantibodies (glutamic acid decarboxylase 65 and tyrosine phosphataserelated islet antigen 2 (IA-2)) documented in NIH CRIS chart or via outside laboratory assessment within the last 10 years.
- 5. Hemoglobin A1C <8% at study initiation

3.3.2 Exclusion Criteria

- 1. Pregnancy or breastfeeding
- 2. Allergy to study medications
- 3. Allergy or self-reported intolerance to blueberry, pomegranate, or oats, soy, gluten or dairy products.
- 4. Chronic insulin therapy or insulin use within the last 3 months
- 5. Treatment with other medications which are known to affect the parameters under study, including antibiotics within the last month, immunosuppressants, proton-pump inhibitors, supraphysiologic systemic steroids, probiotic or prebiotic supplements
- 6. Heavy yogurt consumption (2 or more servings of ≥ 6 oz per day)
- 7. Chronic GI disease, gastric bypass surgery, cancer diagnosis or autoimmune disease

- 8. Metabolic derangement such as metabolic acidosis, severe hyperglycemia (fasting blood glucose \geq 200mg/dL), and/or liver enzymes > three times the upper limit of normal.
- 9. Any other condition that, in the opinion of the investigators, will increase risk to the subject, or impede the accurate collection of study-related data.
- 10. Body weight \geq 450lbs
- 11. Body weight ≤58kg
- 12. Hemoglobin concentration <10g/dL

3.3.3 Rationale for Inclusion Criteria

Age Range 10-25 years and pubertal status

The age range of 10-25 years was chosen to maximize recruitment and includes a wide range of youth afflicted with type 2 diabetes. All participants will be pubertal or post-pubertal youth (defined as Tanner stage IV-V for girls and testicular size 11-25cc for boys) to minimize any potential differences in gut microbiota associated with insulin resistance of puberty. We believe this approach is reasonable because we will have a well-defined cohort (by pubertal status). In addition, the broad content of the microbiome is of similar structure after 3 years old until later adulthood [29] Pubertal status will be defined based on breast examination (Tanner stage IV-V) in girls and testicular examination (11-25cc) in boys. Pubic hair and bone age will not be used to characterize pubertal stage.

Diabetes diagnosis criteria and HbAlc <8%

Type 2 diabetes in youth will be diagnosed according to ADA criteria [36] and eligibility criteria were based on the Treatment Options for Type 2 Diabetes in Adolescents and Youth (TODAY) study design [37]. Youth with HbA1c \geq 8% often have severe hyperglycemia and glucotoxicity which is associated with increased risk for dehydration and ketoacidosis and these conditions may be associated with. changes in the microbiome [38, 39].

3.3.4 Rationale for Exclusion Criteria

Pregnancy and Breastfeeding

Pregnancy and breastfeeding are associated with physiologic increases in insulin resistance, which would confound data interpretation. In addition, the DXA scan cannot safely be performed in pregnant women. Female participants of childbearing age who meet other eligibility requirements and wish to participate in the study will be informed of the potential risks to a pregnancy conceived while on any study medication. Participants who consent to participate will be asked to practice reliable birth control including systemic hormones and/or barrier methods. Patients who are pregnant and/or sexually active and not using adequate birth control will be excluded from enrollment in the trial. Pregnancy tests will be obtained from all female participants before inpatient visits and right before DXA scans. If a subject becomes pregnant while on study they will be removed from the study and will not be allowed to re-enroll on the study

Chronic insulin therapy

Participants who are currently taking insulin therapy or who are within 3 months of insulin treatment will be excluded from the study, as the run-in period would be riskier for these individuals.

Chronic GI diseases or medications/supplements affecting the GI tract

Individuals who have a disease, such as known autoimmunity, inflammatory bowel disease or celiac, may have altered gut microbiota due to that underlying condition. Certain medications are known or theorized to influence the gut milieu, and so to avoid confounding in this small study, we will exclude these patients as well. Additionally, yogurt or other pre/probiotic supplements will change the gut microbiome.

Any condition which may increase risk to the subject or impede accurate data collection

Examples include participants with a history of active thyroid disease, liver disease, pancreatitis, nephrotic syndrome or lupus.

Weight \geq 450lbs

Individuals with weight \geq 450lbs will be excluded because the maximum weight for the dual energy absorptiometry (DXA) scan is 450lbs.

